## **Letters from the IDSMB**

A formal letters containing the recommendations for continuation and action items/modifications will be prepared by the IDSMB chair and coordinators and will be sent to the IDSMB members and principal investigator. It is the responsibility of the PI to distribute the meeting summary to all co-investigators, the study sponsor, and to the IRB during the study's annual review.

## **Communication with the IDSMB/Access to Interim Data**

Access to the accumulating endpoint data will be limited to as small a group as possible. Limiting the access to interim data to the IDSMB members will relieve the PI of the burden of deciding whether it is ethical to continue to randomize participants and will help protect the study from bias in participant entry and/or evaluation.

### *Confidentiality*

The study visits will be conducted at the CTRC at Magee-Womens Hospital, which is equipped to ensure the protection of patient privacy. The collection of sensitive information about participants will be limited to the amount necessary to achieve the aims of the research so that no unnecessary sensitive information is collected.

Paper-based records will be kept in a secure location and only be available to study personnel. Computer-based files will be made accessible to study personnel by access privileges and passwords. Prior to accessing any study-related information, personnel will be required to sign statements agreeing to protect the security and confidentiality of identifiable information. Whenever feasible, identifiers will be removed from study-related information and data.

If a participant withdraws from the study, any personal medical information that was recorded or samples obtained for the research study before the withdrawal may continue to be used by the study.

During data collection, the personal identifiers on study questionnaires and samples are replaced by a unique study ID. After the required data retention period, the link between the assigned study ID and the participant's identity will be destroyed so that nothing can be tracked back to the individual. The data will then be rendered completely anonymous.

## **Adverse Event Reporting Guidelines**

During the course of the study, all adverse events (AEs) and serious adverse events (SAEs) will be monitored, documented, and if causal, reported to the IDSMB and IRB. AEs and SAEs will be captured in the study database using the Adverse Events form. The form will prompt study staff to notify the PI of SAEs for review. Every effort will be made to follow a participant who has had a negative reaction to any study intervention or procedure.

### **Adverse Events (AEs)**

An adverse event (AE) is any unfavorable medical occurrence, which may include abnormal signs (e.g., abnormal physical exam or laboratory finding), symptoms, or disease, temporally associated with, but not necessarily considered related to, the participant's participation in the study. These events are usually of a non-serious nature and are not reportable in accordance with the University of Pittsburgh Institutional Review Board's (IRB) guidelines for "Reportable Events" as they do not pose a risk to study participants.

Adverse events that take place during the course of the study will be classified under the Common Terminology Criteria for Adverse Events (CTCAE), a descriptive terminology used for Adverse Event (AE) reporting. AEs will be categorized as expected or unexpected, in terms of the nature, severity, or frequency, as outlined in the consent form. AEs will be graded using the CTCAE system and relatedness assessed by the PI, and presented to the IDSMB members at IDSMB meetings.

### **Serious Adverse Events (SAEs)**

[figure not shown]
Serious adverse events (SAEs) or "unanticipated problems involving risk to participants or others" are characterized as symptoms which are harmful to the participant and result in significant outcomes, which are reportable to the IRB and IDSMB.

Examples of serious adverse events include:

- Death
- Life-threatening medical events that place a participant at immediate risk of death from the event as it occurred
- Results in inpatient hospitalization or prolongation of existing hospitalization
- Results in persistent or significant disability or incapacity as a result of the study intervention

- Events that, based upon appropriate medical judgment, may jeopardize the participant’s health, and may require medical or surgical intervention to prevent one of the other outcomes listed in this definition

The flow chart below provides an algorithm for determining whether an adverse event meets the definition of an “unanticipated problems involving risk to participants or others”:

Adverse Events which follow the above figure, that meet the criteria of unexpected, fatal or life- threatening, and related or possibly related to the research intervention must be reported to the IRB and the IDSMB Chair and Safety Officer ([name]) within 24 hours of learning of the event. If necessary, a subsequent follow-up report with the details of the event will be submitted as well.

All other reportable adverse events will be submitted to the IRB within 10 business days of the investigator learning of the event. Reportable events will be submitted through the University of Pittsburgh IRB’s PittPRO system; the “Reportable Event” online submission process must be used in order to submit a report. The smart form questions will prompt a response to questions related to the adverse event.

[figure not shown]
SAE and AE reporting guidelines and further instructions on submitting a report in the PittPRO system can be found in the University of Pittsburgh website, <http://www.irb.pitt.edu/>.

### **AE and SAE Assessment Guidelines Specific to the GDM Trial**

Key Criteria: to determine if the event is unexpected, related to participation in the research study and involves risk to human participants or others.

If an adverse event meets the criterion of unexpected, related or possibly related, and poses risk of harm to other participants, study staff will notify the principal investigator within 24 hours, who will then inform and the IDSMB Chair and Safety Officer ([name]). [name] will review and submit the event to the IDSMB, who will discuss the IDSMB recommendations and submit the SAE to the University of Pittsburgh IRB.

In cases of an SAE, the following schematic is to be used:

To evaluate GDM2 Study AEs and SAEs, a licensed medical professional will apply the following assessment criteria:

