#### *IDSMB Responsibilities*

The initial responsibility of the IDSMB was to approve the GDM2 Study. The IDSMB met for the first time on February 25, 2015, to review the Institutional Review Board (IRB) approval letter and IRB-approved protocol and informed consent document. The IDSMB voted and approved the study to begin.

The IDSMB agreed to meet every 6 months during the course of the study to:

1. Review the research protocol, informed consent document, and plans for data and safety monitoring;
2. Evaluate the progress of the study, including periodic assessments of data quality and timeliness, participant recruitment, accrual and retention, participant risk vs. benefit, adverse events, unanticipated problems, performance of the trial sites, and other factors affecting study outcomes;

3. Consider factors external to the study when relevant information becomes available, such as scientific or therapeutic developments that may have an impact on the safety of participants or the ethics of the study;
4. Review clinical center performance, make recommendations, and assist in the resolution of problems reported by the PI;
5. Protect the safety of the study participants;
6. Report on the safety and progress of the study;
7. Make recommendations to the PI, and if required, to the NIH, concerning continuation, termination, or other modifications of the study based on the observed beneficial or adverse effects of the treatment under study;
8. Monitor the confidentiality of the study data and the results of monitoring;
9. Assist the PI by commenting on any problems with study conduct, enrollment, sample size, and/or data collection.

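### For unexpected, related, fatal or life-threatening events that put other participants at risk, the trial-specific reporting route does not ensure the protocol's own 24-hour report to the IRB and the IDSMB Chair

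*Protocol*

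**What the plan says.** Two adjacent sections of the Protocol govern expedited reporting.

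*Serious Adverse Events (SAEs)* sets two deadlines. Events "that meet the criteria of unexpected, fatal or life- threatening, and related or possibly related to the research intervention" are the urgent class, and they "must be reported to the IRB and the IDSMB Chair and Safety Officer ([name]) within 24 hours of learning of the event". A later follow-up report with details is allowed if needed. For the rest, "All other reportable adverse events will be submitted to the IRB within 10 business days of the investigator learning of the event".

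*AE and SAE Assessment Guidelines Specific to the GDM2 Trial* sets a route for events that are "unexpected, related or possibly related, and poses risk of harm to other participants". Its first step is that "study staff will notify the principal investigator within 24 hours, who will then inform and the IDSMB Chair and Safety Officer". A named person, whose identity is masked in the public text, then reviews the event and passes it to the IDSMB, "who will discuss the IDSMB recommendations and submit the SAE to the University of Pittsburgh IRB". The section goes on to refer to an SAE schematic, which is not reproduced in the text available for this review.

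**The concern.** The two definitions overlap. An event that is unexpected, at least possibly related, life-threatening and a risk to other women falls under both sections. One requires the IRB and the IDSMB Chair and Safety Officer to have the report within 24 hours. The other lets the same 24 hours pass before the PI is told, puts the IDSMB before the IRB, and gives no limit for anything that follows.

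Staff can be expected to follow the trial-specific section, and they could follow it fully while missing the deadline in the section before it, for both recipients. At stake is timely independent oversight of the gravest events this manual foresees, in a trial whose investigators are otherwise kept blinded to arm and outcomes.

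**Working it through.** No sample size, power or error rate is involved. The check is a comparison of the two texts and a sum of times.

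**Which events are affected**

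| Feature | SAE section, 24-hour rule | Trial-specific section |
|---|---|---|
| Unexpected | required | required |
| Related or possibly related | required | required |
| Fatal or life-threatening | required | not mentioned |
| Risk to other participants | not mentioned | required |

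The conflict concerns events with all four features. Other reportable events have 10 business days to reach the IRB, and a 24-hour step from staff to PI does not conflict with that.

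**Time to report under the trial-specific route**

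- t1, staff to PI: 0 to 24 h (stated upper limit)
- t2, PI to IDSMB Chair and Safety Officer: no limit stated
- t3, review and IDSMB discussion: no limit stated
- t4, submission to the IRB: no limit stated

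Time to Chair = t1 + t2. Time to IRB = t1 + t2 + t3 + t4. The SAE section requires each to be at most 24 h.

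**When the clock starts.** The 24-hour sentence does not say whose learning of the event counts. The 10-business-day sentence does name the investigator, but those words belong to that rule alone. Both readings therefore need checking.

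*Clock starts when study staff learn of the event.* The time left after step one is 24 − t1.

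- t1 = 24 h: 24 − 24 = 0 h left for t2 + t3 + t4. The route has been followed and the deadline is missed for the IRB and, for any t2 above zero, for the Chair.
- t1 = 1 h: 24 − 1 = 23 h left. The deadline is met only if the Chair, IDSMB and IRB steps all finish within 23 h, which nothing requires.

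*Clock starts when the investigator learns of the event.* Step one uses none of the allowance and 24 h remain. The IDSMB step still comes before the IRB report and is still untimed, so the deadline is again not secured.

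On either reading the route permits a late report. On neither does it force one.

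**The case against.** The best defence has four parts.

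1. *The 24 hours to the PI is a ceiling, not a duration.* Other sections work faster. The Adverse Event form prompts staff to notify the PI of SAEs (Adverse Event Reporting Guidelines) and prompts immediate study-physician review and helps with any notice to the board or the IRB (Visit 1, 2 and 3 Forms). The Chair may call an emergency meeting at any time (IDSMB Board Process). This stands against any claim that the deadline is bound to be missed. It does not remove the conflict: the prompts speed up internal review but set no time for the IRB report, and the emergency meeting is optional and untimed.

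2. *The two sections can be read together.* The 24-hour rule is unconditional, a follow-up report is allowed, and the trial-specific section does not suspend the rule. On this reading an initial report goes out at once and IDSMB review follows. That is a sensible intention, but the trial-specific section does not say so. It makes no exception for fatal or life-threatening events, does not point back to the deadline, and lists the IRB last.

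3. *The start of the clock is unstated.* This is correct, and it weakens the arithmetic for step one. It does not rescue the untimed IDSMB step, and the ambiguity itself needs resolving.

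4. *The schematic and other figures are not shown and may carry timings or parallel paths.* This is a real limit on certainty. Even so, the sentences as written would need to agree with any such figure.

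**Conclusion.** The point holds in a narrow form. For events that are unexpected, related or possibly related, fatal or life-threatening, and a risk to other participants, the two sections conflict, and following the trial-specific one does not ensure the 24-hour report to the IRB and the IDSMB Chair. If the clock starts with staff, the time left for all later steps ranges from 24 h down to 0 h. If it starts with the investigator, 24 h remain for steps that have no limit. The conclusion assumes that the missing schematic does not settle the matter. Such events are probably rare in a trial of glucose tolerance tests, though the documents give no rate.

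A reader might infer three stronger things that the documents do not support.

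- *That the deadline cannot be met.* It can be, if the steps are fast.
- *That the board itself submits to the IRB.* The sentence is ambiguous and the person's role is masked, so the text shows only that the submitting role is unclear.
- *That IDSMB recommendations are withheld from the IRB until annual review.* The section Letters from the IDSMB has the PI distribute the meeting summary to the IRB at that review. It does not say that an urgent recommendation waits for it, and no other section contradicts it. That is a separate matter and no part of this finding.

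**What to change.** Reconcile the trial-specific section with the SAE section. For events meeting both definitions, state that:

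- the initial report goes to the IRB and to the IDSMB Chair and Safety Officer within 24 hours of first awareness by any study staff member, which also settles when the clock starts;
- this report does not wait for IDSMB review;
- the IDSMB recommendation is sent afterwards, as the follow-up report that the SAE section already allows;
- a named role is responsible for submission to the IRB.

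Check the schematic against the revised wording so that text and figure agree. The 10-business-day rule for other reportable events needs no change on this account.

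The cost is manual wording and a short notice to staff. No new procedure, visit or data item is needed.

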#### *Unexpected Medical Events*

These are medical events that are not described in the current IRB-approved protocol or informed consent, taking into account the characteristics of the participant population being studied (i.e. pregnant women).

### *Expected Medical Events*

- Symptoms and risk related to normal pregnancy progression such as nausea, vomiting, fatigue, urinary frequency, increased or decreased appetite, transient dizziness, mild back or breast pain or discomfort, mild mood changes, miscarriage, preterm delivery, stillbirth, low birth weight, problems with placenta, and birth defects
- Symptoms related to fasting for at least 8 hours and related hypoglycemia: headache, nausea, and lightheadedness
- Symptoms related to hypoglycemia such as fainting, fast heart rate, sweating, shakiness, difficulty paying attention, sudden moodiness or irritability, loss of consciousness
- Symptoms related to venous blood draw such as bruising, bleeding, swelling, and pain, fainting, lightheadedness, and infection at the injection site
- Symptoms related to consuming the glucose solution for the diabetes testing such as brief nausea, vomiting, tiredness, lightheadedness, and upset stomach

While the above medical events may be expected, they will be collected for outcome purposes.

### *Event Severity using Common Terminology Criteria for Adverse Events (CTCAE)*

Grade refers to the severity of the AE. The CTCAE displays Grades 1 through 5 with unique clinical descriptions of severity for each AE based on these general guidelines:

- Grade 1: Mild; asymptomatic or mild symptoms; clinical or diagnostic observations only; intervention not indicated.
- Grade 2: Moderate; minimal, local or noninvasive intervention indicated limiting age- appropriate instrumental activities of daily living.
- Grade 3: Severe or medically significant but not immediately life threatening; hospitalization or prolongation of hospitalization indicated; disabling; limiting self-care.
- Grade 4: Life-threatening consequences; urgent intervention indicated.
- Grade 5: Death related to AE.

### *Event Relatedness*

Very Likely Related: The incident, experience, or outcome is more likely than not caused study procedures.

- A reasonable time course would be within the 1-4 hours the participant is receiving oral glucose tolerance testing.
- Symptoms abate once the study product is discontinued and patient has received a snack or drink.
- Symptoms are not explained by other factors such as concomitant medications or current illness

Probable: There is reasonable possibility that the incident, experience or outcome may have been caused by study procedures.

- A reasonable time course would be within 24 hours the participant either fasting for the study or receiving the oral glucose tolerance testing.
- Symptoms may be explained by other factors such as concomitant medications or current illness

Possible: There is a possibility that the incident, experience or outcome may have been caused by study procedures.

- A reasonable time course would be within 25-48 hours the participant fasting for the study, receiving the OGTT, or final blood draw.
- Symptoms may be explained by other factors such as concomitant medications, current illness, or other healthcare procedures.

Doubtful: There is a reasonable doubt that the incident, experience or outcome was not caused by study procedures.

- Symptoms may be explained by other factors such as concomitant medications, current illness, or other healthcare procedures.

Not Related: There is complete assurance that the incident, experience or outcome could not have been caused by any study procedures.

## **Study Completion and Closeout**

### **Study Completion and Closeout Procedures**

This study will be complete when the target enrollment number has been reached and all research procedures have been completed, or allotted time to complete the study has passed. If the investigator is no longer using identifiable data for analysis, the study completion process may be initiated as no further IRB oversight is required. The study will not close until the sponsor conducts the final closeout visit, as an intervention or interaction with participants may be needed to complete the research data.

The investigator must submit a final report for the Early Termination or Study Completed activities for IRB review via the PittPRO website.

#### **The following are to be addressed to the IRB for the final report:**

- Since the study began, how many participants have been entered into this research study at all sites under the authority of the University of Pittsburgh IRB? Do not include those participants who failed to meet the inclusion criteria during screening.
- Total number of participants approved to undergo research related procedures at all sites under the authority of the University of Pittsburgh IRB.
- Did participant accrual reflect the ethnic and racial demographics of Pittsburgh and the surrounding area and/or the relevant patient population of the UPMC; or the demographics of the alternate site(s) where this research is being conducted?
- Have there been any unanticipated problems that were not previously reported that meet the University of Pittsburgh reporting guidelines? If yes, you must immediately submit an unanticipated problem report, which must be available for the IRB's consideration during review of this final report.
- Have you already provided, or do you plan to provide, your study participants with a summary of study results?
- Summarize the outcomes and conclusions of this study. Describe the extent to which the specific aims of this study were addressed and discuss the study's impact on the relevant scientific/medical issues.

A final Data and Safety Monitoring Plan (DSMP) report is to be uploaded into PittPRO as described in the approved study.

### **Early Termination of Study**

The study may be canceled or stopped prematurely before targeted enrollment numbers have been reached and/or all required research procedures have been completed. The study sponsor, PI, federal agency, or local IRB may terminate the study early for reasons including but not limited to: change in risk/benefit assessment, loss of funding, new information, etc.

### **Retention of Study Documentation**

The investigators may continue to use and disclose, for research purposes, identifiable information related to participation in this research study for a minimum of five years after final reporting or publication of a project. Following the required data retention period, secured long-term retention of any documents will occur and they will be rendered anonymous. The majority of documents (both electronic and paper) will be de-identified from the start of the study. After the study has been closed, study-related files may be given to the PI for long-term storage.

## Table of Changes from Version IV to Version V

Pg	Header	Description of Change
-	-	Updated: All references to WePay changed to “University issued payment card” (WePay system phased out end of 2018 and replaced with Vincent system)
-	-	Removed: All references to study ID card (did not use)
-	-	Updated: All references to OSIRIS changed to PittPRO – new IRB system
-	-	Updated: All references to Heinz Lab (closed in 2018) changed to UPMC Clinical Laboratory Building (CLB)
vii- viii	List of Abbreviations	Updated: List of Abbreviations
10- 11	GDM2 Co- Investigators	Updated: Contact information for [name] and [name]
14	GDM2 Principal Study Staff	Removed: Project Coordinator ([name])
14- 15	GDM2 Principal Study Staff	Updated: Study staff responsibilities after departure of coordinator
16	GDM2 Clinical Team	Removed: GSPH Heinz Laboratory Director ([name]) and Manager ([name])
17	GDM2 Clinical Team	Updated: Replaced [name] with [name] (MWRI Lab Liaison)
18	GDM2 Data Center Staff	Added: [name] (CRHC-DC Data Analyst)
19	GDM2 Regulatory Staff	Updated: Replaced [name] with [name] (IRB)
24	Recruitment Plan	Added: Added WomanCare, Wiesenfeld/Updike, UOA NIA, OGAP, and OPC clinics in list of clinics
24	Recruitment Plan	Removed: OPC Purple and Western PA Women’s Health
24	Recruitment Plan	Updated: Identified clinics as public or private providers
25	In-Clinic Recruitment	Removed: Introductory letter recruitment (did not use)
25- 26	Additional Recruitment Methods	Added: WIC Office, list of UPMC hospitals, digital message boards
27	Screening Procedures	Updated: Clarified that dumping syndrome caused by gastric bypass surgery precludes participation, not gastric bypass surgery per se

27	Screening Procedures	Updated: Clarified severe liver disease indicated by elevated AST/ALT values
28	Hypertension and Corticosteroid Medications	Updated: Clarified that low-dose or baby aspirin (LDASA or BASA) is acceptable
28	Hypertension and Corticosteroid Medications	Updated: Added list of common hypertension and corticosteroid medications
31	Magee-Womens Hospital Clinical and Translational Research Center	Updated: Corrected location of MWH CTRC
32	50 gram Glucose Challenge Test	Added: Study samples are tubed from MWH to UPMC CLB for testing
33	IV Protocol	Added: Section regarding use of MWH IV team for study visits
34	Visit 1 Forms	Removed: Positive GDM Results – Notification Form (does not exist in database, notification of providers documented in Form 11 – 50gm Lab and Repeat Lab)
34	Visit 1 Forms	Added: Description of Concomitant Medication Form
35	Critical Glucose Values	Updated: All critical glucose values are documented as Adverse Events (AE); only contacted [name] when database AE form indicated critical value is a Serious Adverse Event (SAE)
36	Blinding	Updated: Clarified cases in which the PI or co-I's are unblinded
37	75 g or 100 g Oral Glucose Tolerance Test	Updated: Latest time Visit 2 scheduled is 11:30 am instead of 11:00 am
37	75 g or 100 g Oral Glucose Tolerance Test	Added: Study samples are tubed from MWH to UPMC CLB for testing
38	Visit 2: IV Protocol	Added: Use of MWH IV team for study visits
39	Visit 2 Forms	Added: Postpartum Depression Questionnaire – Score of 13 OR answer of anything other than “Never” to Question 10 regarding thoughts of self-harm
39	Visit 2 Forms	Updated: 24-Hour Dietary Recall Telephone - Follow-up dietary recall to be completed at either 32w0d or up to 2 weeks after Visit 2

39	Visit 2 Forms	Removed: 75gm or 100gm Repeat Fasting Glucose Lab Form – integrated into Form 14 ; 75gm or 100gm Fasting Glucose Lab
39	Visit 2 Forms	Removed: Positive GDM Results – Notification Form (does not exist in database, notification of providers documented in Form 14 – 75gm or 100gm Fasting Glucose Lab)
40	Visit 2 Forms	Added: Description of Concomitant Medication Form
40	Postpartum Depression Questionnaire	Updated: Study staff offer to contact providers to notify of high EPDS score, and offer resources; in severe cases, will be reported as SAE
41	75 g or 100 g OGTT Laboratory Results	Updated: “C-reactive peptide” to high sensitivity C-reactive peptide
41	75 g or 100 g OGTT Laboratory Results	Removed: Cytokines run at Visit 2 (not run in real time at Visit 2)
41	75 g or 100 g OGTT Laboratory Results	Updated: Clarified 75 g OFTT diagnosis is $\geq 1$ ( one or more ) abnormal value(s); 100 g OGTT diagnosis is $\geq 2$ ( two or more ) abnormal values (previously noted as only 1 or only 2)
41-42	“Mild GDM”	Added: Section regarding “Mild GDM” results
42	Unblinding Providers to OGTT Results	Added: Citation for HAPO Study
42	Critical Glucose Values	Added: Any results indicating hypo- or hyperglycemia are reported as Adverse Events
43	Visit 2 Results Back Entry	Added: Section regarding back entry of Visit 2 results to participants’ EMR, for clinical use post-study
44	Delivery Time Point	Added: OSPU also does not collect specimens in cases of medical emergency or precipitous delivery
44	Infant PEA POD Assessment	Removed: Entire section – PEA POD never used in study due to unavailability (substituted skinfold measurements instead)
44	Infant Skinfold Measurement	Updated: Infant skinfold measurements will be obtained between 24-48 hours after delivery
44	Infant Skinfold Measurement	Added: Parents may also refuse skinfold measurements
47	3, 6, and 9 Month Postpartum Forms	Added: Description of Infant Status Form
49	Visit 3 IV Protocol	Added: Use of MWH IV team for study visits

50	Visit 3 Forms	Removed: Positive GDM Results – Notification Form (does not exist in database, notification of providers documented in Form 14 – 75gm Fasting Glucose Lab)
51	Visit 3 Forms	Added: Description of Infant Status Form and Concomitant Medication Form
51	Visit 3 Questionnaires and Assessments	Added: Participants who are pregnant at Visit 3 may choose to have their 75 g OGTT results sent to their OB provider in lieu of their regular GDM testing
52	Postpartum Depression Questionnaire	Updated: Study staff offer to contact providers to notify of high EPDS score, and offer resources; in severe cases, will be reported as SAE
52	Completing Visit 3	Updated: Follow-up dietary recall is not scheduled, to avoid biasing patient
53	Visit 3 Laboratory Results	Updated: Clarified diagnostic criteria for impaired glucose tolerance and Type 2 diabetes ( one or more abnormal values)
53-54	Visit 3 Laboratory Results	Added: Database will also prompt staff to notify PI of high triglycerides or cholesterol values, to notify participant
54	Visit 3 Results Back Entry	Added: Section regarding back entry of Visit 3 results to participants' EMR, for clinical use post-study
54	Quest Diagnostics Visit	Updated: Clarified that participants will complete a 75 g OGTT at Quest Diagnostics, and option is only available for Visit 3
55-57	Data Abstraction	Updated: CARE service has been replaced by Health Record Research Request (R3) service
56	Data Collection Associated with Study Outcomes	Added: ICD-10 procedure and diagnostic codes also used in R3 data abstraction
58-62	Laboratory Procedures and Protocols	Updated: Study staff handle all lab procedures, did not use research technician
58	Specimen Collection	Added: Section listing specimens collected at each visit
59-60	Visit 2 Laboratory Procedures	Updated: Cytokine labs not run in real time; analyzing lab TBD by PI
61	Visit 3 Laboratory Procedures	Updated: Cytokine labs not run in real time; analyzing lab TBD by PI
62	Visits 2 and 3 Occurring on Saturdays	Added: Section regarding special specimen collection and laboratory procedures for Visits 2 and 3 occurring on Saturdays

63-64	Specimen and Laboratory Flow Charts	Updated: Specimen and Laboratory Flow Charts; cytokine labs not run in real time, analyzing lab TBD
67-68	Clinical Laboratory Protocols	Updated: Cytokine processing procedures and lab TBD
69	Adherence and Retention	Removed: Study website and Facebook page never implemented
